^a Assessments will take place 60-30 minutes before dosing or in the morning on nondosing days.

^b Drop comfort assessments will be obtained immediately, 1, 2, and 3 minutes after instillation of the investigational product; to be assessed at morning doses only. If the score is not ≤3 at minute 3, the drop comfort assessment should be repeated at minutes 5, 10, and 15 until the score is ≤3. If the score is >3 at minute 15, it should be recorded as an adverse event.

^c Slit lamp examination of anterior segment will be performed only during the morning assessment on the following days: Screening, Day -14, SDTP Day -2, SDTP Day -1, MDTP Day -2, MDTP Day -1, and Day 29.

^d At screening IOP may be done at any time during the day. At MWOA (D-14), IOP should be done at 10:00am ±3 hours. IOP only needs to be done at one time during screening, MWOA, and Day 29.

^e Gonioscopy at screening can be done at any time of day. Gonioscopy on Day 29 will be performed at the morning time point.

^f Ophthalmologic assessments on screening, MWOA (D-14), and Day 29 need to be done one time during the day only.

These assessments include: BCVA, Manifest Refraction (Screening), Slit Lamp examination of anterior segment, Conjunctival Redness, Corneal Haze, Corneal Epithelial integrity using fluorescein stain, Anterior Chamber cell and flare, Lens Opacification, IOP, Posterior Segment Examination, dilated (Screening and Day 29), Specular Microscopy, Noncontact (Screening and Day 29), Corneal Pachymetry (Screening and Day 29)

^g Subjects will be administered the last dose of study drug on the morning of Day 28.

^h ECG is to be performed at one time point only on Day 26 and Day 29

Timings relate to dose administration or the equivalent morning assessment. Refer to Section 7.1 for guidance on the priority order of assessments. Assessments on nondosing days (screening, baseline, and Day 29) will take place once in the morning only unless otherwise specified.

Table 3 Detailed Schedule of Events – Cohort B

Assessment	Days Performed (Screening through D29) ^f	Predose/ Morning ^a										
			0 m	30 m	1 h	2 h	3 h	4 h	6 h	8 h	12 h	
Assessment Window (minutes)			0	±5	±15	±15	±15	±15	±15	±15	±15	±15
Alcohol breath test	SCR, D-14, D-2, D-1, D1, D14, D21, D26	X										
Serum pregnancy test (female subjects)	SCR, D-2 D1, D26, D29.	X										
Biochemistry, hematology, and urinalysis	SCR, D-2, D1, D7, D14, D21, D26, D27, D29.	X										

Ab=antibody; BCVA=best-corrected visual acuity; D=day; ECG=electrocardiogram; FU=follow up; h=hours; IOP=intraocular pressure; m=minutes; MDTP=multiple-dose treatment period; PK=pharmacokinetic; SCR=screening.

^a Assessments will take place 60-30 minutes before the first dose of the day or in the morning on nondosing days.

^b Drop comfort assessments will be obtained immediately, 1, 2, and 3 minutes after instillation of the investigational product; to be assessed at morning doses only. If the score is not ≤3 at minute 3, the drop comfort assessment should be repeated at minutes 5, 10, and 15 until the score is ≤3. If the score is >3 at minute 15, it should be recorded as an adverse event.

^c Slit lamp examination of anterior segment will be performed only during the morning assessment on the following days: Screening, Day -14, Day -2, Day -1 and Day 29.

^d At screening IOP may be done at any time during the day. At MWOA (D-14), IOP should be done at 10:00am ±3 hours. IOP only needs to be done at one time during screening, MWOA, and Day 29.

^e Gonioscopy at screening can be done at any time of day. Gonioscopy on Day 29 will be performed at the morning time point.

^f Ophthalmologic assessments on screening, MWOA (D-14), and Day 29 need to be done one time during the day only.

These assessments include: BCVA, Manifest Refraction (Screening), Slit Lamp examination of anterior segment, Conjunctival Redness, Corneal Haze, Corneal Epithelial integrity using fluorescein stain, Anterior Chamber cell and flare, Lens Opacification, IOP, Posterior Segment Examination, dilated (Screening and Day 29), Specular Microscopy, Noncontact (Screening and Day 29), Corneal Pachymetry (Screening and Day 29).

^g Subjects will be administered the last dose of study drug on the morning of Day 28.

^h ECG is to be performed at one time point only on Day 26 and Day 29.

Timings relate to the first dose of the day or the equivalent morning assessment. Refer to Section 7.1 for guidance on the priority order of assessments. Assessments on nondosing days (screening, baseline, and Day 29) will take place once in the morning only unless otherwise specified.

Table 4 Detailed Schedule of Events – Cohort C

Assessment	Days Performed (Screening through D29) ^f	Predose/ Morning ^a	0 m	30 m	1 h	2 h	3 h	4 h	6 h	8 h	12 h
Assessment Window (minutes)			0	±5	±15	±15	±15	±15	±15	±15	±15
Drugs of abuse	SCR, D-14, D-2, D-1, D1, D14, D21, D26.	X									
Alcohol breath test	SCR, D-14), D-2, D-1, D1, D14, D21, D26.	X									
Serum pregnancy test (female subjects)	SCR, D-2, D1, D26, D29.	X									
Biochemistry, hematology, and urinalysis	SCR, D-2, D1, D7, D14, D21, D26, D27, D29.	X									

Timings relate to the first dose of the day or the equivalent morning assessment. Refer to Section 7.1 for guidance on the priority order of assessments. Assessments on nondosing days (screening, baseline, and Day 29) will take place once in the morning only unless otherwise specified.

Ab=antibody; BCVA=best-corrected visual acuity; D=day; ECG=electrocardiogram; FU=follow up; h=hours; IOP=intraocular pressure; m=minutes; MDTP=multiple-dose treatment period; PK=pharmacokinetic; SCR=screening

^a Assessments will take place 60-30 minutes before the first dose of the day or in the morning on nondosing days.

^b Drop comfort assessments will be obtained immediately, 1, 2, and 3 minutes after instillation of the investigational product; to be assessed at morning doses only. If the score is not ≤3 at minute 3, the drop comfort assessment should be repeated at minutes 5, 10, and 15 until the score is ≤3. If the score is >3 at minute 15, it should be recorded as an adverse event.

^c Slit lamp examination of anterior segment will be performed only during the morning assessments on the following days: Screening, Day -14, Day -2, -Day 1, and Day 29.

^d At screening IOP may be done at any time during the day. At MWOA (D-14), IOP should be done at 10:00am ±3 hours. IOP only needs to be done at one time during screening, MWOA, and Day 29.

^e Gonioscopy at screening can be done at any time of day. Gonioscopy on Day 29 will be performed at the morning time point.

^f Ophthalmologic assessments on screening, MWOA (D-14), and Day 29 need to be done one time during the day only.

These assessments include: BCVA, Manifest Refraction (Screening), Slit Lamp examination of anterior segment, Conjunctival Redness, Corneal Haze, Corneal Epithelial integrity using fluorescein stain, Anterior Chamber cell and flare, Lens Opacification, IOP, Posterior Segment Examination, dilated (Screening and Day 29), Specular Microscopy, Noncontact (Screening and Day 29), Corneal Pachymetry (Screening and Day 29).

^g Subjects will be administered the last dose of study drug on the morning of Day 28.

^h ECG is to be performed at one time point only on Day 26 and Day 29.

Timings relate to the first dose of the day or the equivalent morning assessment. Refer to Section 7.1 for guidance on the priority order of assessments. Assessments on nondosing days (screening, baseline, and Day 29) will take place once in the morning only unless otherwise specified.

Table 5 Detailed Schedule of Events – Cohort D

Assessment	Days Performed (Screening through D29) ^f	Predose/ Morning ^a									
			0 m	30 m	1 h	2 h	3 h	4 h	6 h	8 h	12 h
Assessment Window (minutes)			0	±5	±15	±15	±15	±15	±15	±15	±15
Corneal pachymetry	SCR, D-1, D1, D2, D7, D14, D29	X			X	X		X			X
Antidrug Ab blood sampling	D-2, D14, D29, D88/FU	X									
Drugs of abuse	SCR, D-14, D-2, D-1, D1, D14, D21, D26.	X									
Alcohol breath test	SCR, D-14, D-2, D-1, D1, D14, D21, D26.	X									
Serum pregnancy test (female subjects)	SCR, D-2, D1, D26, D29.	X									
Biochemistry, hematology, and urinalysis	SCR, D-2D1, D7, D14, D21, D26, D27, D29.	X									

Ab=antibody; BCVA=best-corrected visual acuity; D=day; ECG=electrocardiogram; FU=follow up; h=hours; IOP=intraocular pressure; m=minutes; MDTP=multiple-dose treatment period; PK=pharmacokinetic; SCR=screening

^a Assessments will take place 60-30 minutes before the first dose of the day or in the morning on nondosing days.

^b Drop comfort assessments will be obtained immediately, 1, 2, and 3 minutes after instillation of the investigational product; to be assessed at morning doses only. If the score is not ≤3 at minute 3, the drop comfort assessment should be repeated at minutes 5, 10, and 15 until the score is ≤3. If the score is >3 at minute 15, it should be recorded as an adverse event.

^c Slit lamp examination of anterior segment will be performed only during the morning assessment on the following days: Screening, Day -14, Day -2, Day 1, and Day 29.

^d At screening IOP may be done at any time during the day. At MWOA (D-14), IOP should be done at 10:00am ±3 hours. IOP only needs to be done at one time during screening, MWOA, and Day 29.

^e Gonioscopy at screening can be done at any time of day. Gonioscopy on Day 29 will be performed at the morning time point.

^f Ophthalmologic assessments on screening, MWOA (D-14), and Day 29 need to be done one time during the day only.

These assessments include: BCVA, Manifest Refraction (Screening), Slit Lamp examination of anterior segment, Conjunctival Redness, Corneal Haze, Corneal Epithelial integrity using fluorescein stain, Anterior Chamber cell and flare, Lens Opacification, IOP, Posterior Segment Examination, dilated (Screening and Day 29), Specular Microscopy, Noncontact (Screening and Day 29), Corneal Pachymetry (Screening and Day 29)

^g Subjects will be administered the last dose of study drug on the morning of Day 28.

^h ECG is to be performed at one time point only on Day 26 and Day 29.

Timings relate to the first dose of the day or the equivalent morning assessment. Refer to Section 7.1 for guidance on the priority order of assessments. Assessments on nondosing days (screening, baseline, and Day 29) will take place once in the morning only unless otherwise specified.

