- ^d For the MDTP, subjects in Cohorts A, B, C, and D will arrive at the unit before the morning assessments and depart after the evening assessments on Days -2 and -1. They will be admitted to the unit on the morning of Day 1 and discharged from the unit after completing the Day 2 assessments. They will arrive at the unit before the morning assessments and depart after the evening assessments on Days 7, 14, and 21. They will be admitted to the unit on the evening of Day 26 and discharged from the unit after completing the assessments on the morning of Day 29. While admitted to the unit, subjects must remain within the unit unless otherwise specified.
- ^e The final dose will be at approximately 8:00 AM on Day 28.
- ^f Subjects who are prematurely discontinued from the study will complete the Day 29/ET assessments as fully as possible.
- ^g A follow-up telephone call will take place 7±2 days post discharge from the clinic (Day 29 of MDTP).
- ^h All eligibility criteria except IOP-related criteria (inclusion criterion 4 and exclusion criterion 4) will be assessed at screening.
- ⁱ Excluding Cohort A (previously performed during the SDTP baseline).
- ^j Breathalyzer test for alcohol and urine screening for drugs of abuse.
- ^k These assessments will be performed at initial screening and may also be performed at any visit during the screening period.
- ^l Vital signs include blood pressure, pulse rate, and temperature.

Table 1 Overall Schedule of Events

Study Visit	Screening and WO 1 ^{a,t}		SDTP Baseline ^b		SDTP (Cohort A) ^b		WO 2 ^c	MDTP Baseline ^d		MDTP ^d (Cohorts A, B, C, and D)															
	-28	-14/ MWOA ^f	-2	-1	1	2		-2	-1	1	2	3-6	7	8-13	14	15-20	21	22-25	26	27	28 ^e	29/ ET ^{f,t}	FU Call ^g	88/ FU ^s , v	
Study Day Window (Days)	-14	±2			0	0				0	0		±2		±2		±2						0	±2	±4

^m Drop comfort assessments will be performed immediately and 1, 2, and 3 minutes after instillation of the investigational product; to be assessed at morning doses only. If the score is not ≤3 at minute 3, the drop comfort assessment should be repeated at minutes 5, 10, and 15 until the score is ≤3. If the score is >3 at minute 15, it should be recorded as an adverse event.

ⁿ If BCVA decreases by 6 or more letters, then a dilated posterior segment examination should be performed.

^o Manifest refraction should be repeated if the BCVA in either eye decreases by 10 or more letters.

^p Conjunctival redness will be evaluated using the Efron scale.

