6.2.3.2 Dose Escalation

Throughout the study, dose escalation meetings will commence at regular time points to review safety data and authorize progression into the next cohort. The anticipated dose escalation scheme is presented in Table 10.

- Single-dose cohorts: a dose escalation meeting may convene after a minimum of 6 subjects have completed the 24-hour assessments for the SDTP. At the dose escalation meeting, a preselected Dose Escalation Committee will determine whether it is safe to continue to the anticipated cohort at either the next dose level or the next dosing regimen.
- Multiple-dose cohorts: a dose escalation meeting may convene after a minimum of 6 subjects have completed the Day 14 assessments for the MDTP. At the dose escalation meeting, a preselected Dose Escalation Committee will determine whether it is safe to continue to the anticipated cohort at either the next dose level or the next dosing regimen. If the dose escalation meeting was held prior to the completion of the cohort, the remainder of the treatment period will be completed following the dose escalation meeting.

Table 10 Anticipated Dose-escalation Scheme

Dose Authorized by Committee			Enabling Required Dose-escalation Activity					
			Before Switch from Single to Multiple Dose - BID, TID, or QID			Before Increasing Dose Level		
Cohort	Dose	Regimen	Cohort	Dose	Regimen	Cohort	Dose	Regimen
A1	0.1%/Placebo	SD	NA	–	–	NA	–	–
A1	0.1%/Placebo	QD	A1	0.1%/Placebo	SD	NA	–	–
A2	0.3%/Placebo	SD	NA	–	–	A1	0.1%/Placebo	SD
A2	0.3%/Placebo	QD	A2	0.3%/Placebo	SD	A1	0.1%/Placebo	QD
A3	0.6%/Placebo	SD	NA	–	–	A2	0.3%/Placebo	SD
A3	0.6%/Placebo	QD	A3	0.6%/Placebo	SD	A2	0.3%/Placebo	QD
B1	0.1%/Placebo	BID	A1	0.1%/Placebo	QD	NA	/–	–
B2	0.3%/Placebo	BID	A2	0.3%/Placebo	QD	B1	0.1%/Placebo	BID
B3	0.6%/Placebo	BID	A3	0.6%/Placebo	QD	B2	0.3%/Placebo	BID
C1	0.1%/Placebo	TID	B1	0.1%/Placebo	BID	NA	/–	–
C2	0.3%/Placebo	TID	B2	0.3%/Placebo	BID	C1	0.1%/Placebo	TID
C3	0.6%/Placebo	TID	B3	0.6%/Placebo	BID	C2	0.3%/Placebo	TID
D1 ^a	0.1%/Placebo	QID	C1	0.1%/Placebo	TID	NA	–/	–
D2	0.3%/Placebo	QID	C2	0.3%/Placebo	TID	D1	0.1%/Placebo	QID
D3	0.6%/Placebo	QID	C3	0.6%/Placebo	TID	D2	0.3%/Placebo	QID

BID=twice daily; NA= not applicable; QD=once daily; QID=4 times daily; SD=single dose; TID=3 times daily.

^a Cohort D1 is not to be enrolled as it was decided that the resulting data would not contribute to the understanding of the safety of SHP639.

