7.2.2.3 Ophthalmologic Examination

Ophthalmologic examinations of both eyes will be performed at the visits specified in [Table 1](#); the time points during each visit are specified in [Table 2](#), [Table 3](#), [Table 4](#), and [Table 5](#) for Cohorts A, B, C, and D, respectively. Both eyes will be assessed at each examination unless otherwise specified.

Manifest Refraction

Manifest refraction will be determined at the following visits in order to assess BCVA:

- Screening
- SDTP (Cohort A only): Day -2
- MDTP (all cohorts): Day -2 and Day 29

The manifest refraction will be repeated if the BCVA has decreased by 10 or more letters. Full instructions for performing the manifest refraction are included in the ophthalmology procedures manual.

Best-Corrected Visual Acuity

Using the manifest refraction, the BCVA will be assessed at distance before slit lamp examination at the following visits:

- Screening
- Midwashout assessment
- SDTP (Cohort A only): Days -2 and -1 and Days 1 and 2
- MDTP (all cohorts): Days -2 and -1 and Days 1, 2, 7, 14, 21, 27, 28, and 29

See [Table 2](#), [Table 3](#), [Table 4](#), and [Table 5](#) for detailed timings by cohort.

Full instructions for measuring BCVA are provided in the ophthalmology procedures manual.

A decrease in BCVA by 6 or more letters may be considered clinically significant (CS) or not clinically significant (NCS) and requires a dilated posterior segment examination. A 10-letter loss in BCVA is considered CS and requires a repeat manifest refraction and dilated posterior segment examination. Clinically significant changes should be recorded as AEs in the source document and eCRF.

Slit Lamp Biomicroscopy

Slit lamp biomicroscopy will be performed at the following visits:

- Screening
- Midwashout assessment

- SDTP (Cohort A only): Days -2 and -1 and Days 1 and 2
- MDTP (all cohorts): Days -2 and -1 and Days 1, 2, 7, 14, 21, 27, 28, and 29

See [Table 2](#), [Table 3](#), [Table 4](#), and [Table 5](#) for detailed timings by cohort.

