The anterior segment will be examined through the slit lamp before performing IOP measurements, pachymetry, or graded assessments. The following structures will be evaluated as normal or abnormal. If abnormal, the findings should be described and recorded as either CS or NCS. Any CS findings should be recorded as AEs; the investigator may use his/her discretion to determine whether a finding considered NCS is reported as an AE. Findings and assessment of clinical significance should be recorded in the source documents and eCRF.

The following will be examined at each visit:

- Lids/lashes/lacrimal
- Conjunctiva
- Cornea
- Anterior chamber
- Iris
- Lens

Anterior Segment Graded Assessments

Anterior segment graded assessments will be performed at the following visits:

- Screening
- Midwashout assessment
- SDTP (Cohort A only): Days -2 and -1 and Days 1 and 2
- MDTP (all cohorts): Days -2 and -1 and Days 1, 2, 7, 14, 21, 27, 28, and 29

See [Table 2](#), [Table 3](#), [Table 4](#), and [Table 5](#) for detailed timings by cohort.

Anterior segment graded assessments should be performed during the slit lamp examination but before IOP measurement. The following assessments will be performed:

- Conjunctival redness score assessment
- Corneal haze assessment
- Corneal epithelial integrity assessment by fluorescein staining
- Anterior chamber cell and flare
- Lens opacification (performed during dilated examination only)

The procedures are outlined in [Appendix 2](#); full instructions are provided in the ophthalmology procedures manual.

Any abnormal findings should be described and recorded as either CS or NCS. Any CS findings should be recorded as AEs; the investigator may use his/her discretion to determine whether a finding considered NCS is reported as an AE. Findings and assessment of clinical significance should be recorded in the source document and eCRF.

Intraocular Pressure

Intraocular pressure will be measured at the following visits:

- Screening
- Midwashout assessment
- SDTP (Cohort A only): Days -2 and -1, Days 1 and 2
- MDTP (all cohorts): Days -2 and -1 and Days 1, 2, 7, 14, 21, 27, 28, and 29

See [Table 2](#), [Table 3](#), [Table 4](#), and [Table 5](#) for detailed timings by cohort.

Predose morning IOP assessments must be completed at least 30 minutes before dosing to allow the anesthetic to wear off.

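### Footnote c of the Cohort D schedule (protocol Table 5, repeated in SAP Table 5) prints dosing Day 1 where nondosing Day -1 is meant, so read literally the Day 1 ungraded slit-lamp exam is predose only

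*Protocol*

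**What the plan says.** Protocol Table 5 sets the within-day timing for Cohort D. Its footnote c states that the slit-lamp examination of the anterior segment is "performed only during the morning assessment on the following days: Screening, Day -14, Day -2, Day 1, and Day 29". SAP Table 5 carries the same list, slightly reworded, also with Day 1.

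Two other statements attached to protocol Table 5 bear on how this is read:

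- Footnote a defines the predose/morning column: "Assessments will take place 60-30 minutes before the first dose of the day or in the morning on nondosing days".
- The note under the table states the general rule: "Assessments on nondosing days (screening, baseline, and Day 29) will take place once in the morning only unless otherwise specified".

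Protocol Section 7.2.2.3 lists the slit-lamp visits in the multiple-dose period as "MDTP (all cohorts): Days -2 and -1 and Days 1, 2, 7, 14, 21, 27, 28, and 29" and refers to Tables 2 to 5 for timing. Protocol Table 10 adds that "Cohort D1 is not to be enrolled", which leaves D2 and D3.

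**The concern.** Footnote c is a list of days on which the exam is cut back to a single morning round. That makes sense on days without dosing. On Day 1 it removes any post-dose round of the ungraded exam, which covers lids/lashes/lacrimal, conjunctiva, cornea, anterior chamber, iris and lens.

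This is the first day of the most frequent regimen. At 0.6% four times daily the stated dose margins are the lowest in the protocol: 1-fold in Table 6 and 0.6-fold in Table 7. Protocol Section 1.3 relies on frequent serial eye examinations, slit lamp included, to catch corneal or other effects early. Because Section 7.2.2.3 leaves timing to the tables, the footnote is the operative instruction and a site could act on it.

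**Working it through.** No figure in the plan needs reproducing. The check is a comparison of texts, then a count of what the literal reading touches.

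**1. The eight copies of footnote c**

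| Cohort | Protocol | SAP |
|---|---|---|
| A (Table 2) | Day -1 | Day -1 |
| B (Table 3) | Day -1 | Day -1 |
| C (Table 4) | -Day 1 | Day -1 |
| D (Table 5) | Day 1 | Day 1 |

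Five copies print Day -1, one has the minus sign misplaced, and two print Day 1: 5 + 1 + 2 = 8. Both Day 1 copies are Cohort D. Both keep the minus sign on Day -14 and Day -2 in the same line, so a sign lost in reading the PDF is unlikely. The amendment history in protocol Appendix 1 records no slit-lamp rule specific to Cohort D.

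**2. Which entry fits the table's own rule.** The note under Table 5 names screening, baseline and Day 29 as the once-in-the-morning days. Screening, Day -14, Day -2 and Day 29 all fit, and so would Day -1. Day 1 does not.

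**3. What the literal text does.** Footnote a makes the morning assessment on a dosing day predose. Footnote c with Day 1 in it therefore gives a predose-only structural exam on Day 1.

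**4. Visits affected.** From Day 1 onward the slit-lamp visits are Days 1, 2, 7, 14, 21, 27, 28 and 29, which is 8. All but Day 29 are dosing days, which leaves 7. As printed, the footnote restricts Days 1 and 29; as corrected, Day 29 only. The difference is 1 of 7 dosing-day visits, and 7 - 1 = 6 are untouched.

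**5. Subjects.** 2 cohorts × 7 = 14 planned, of whom 2 × 5 = 10 are on SHP639.

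**6. What remains on Day 1.** Footnote c names only the slit-lamp examination. Footnote f lists redness, haze, fluorescein staining, and cell and flare as separate items, so footnote c does not restrict them. SAP Section 11.6.2.4 gives redness at 1, 3, 6 and 12 h, and SAP Section 11.6.2.6 gives staining at 2, 4, 8 and 12 h. The union is {1, 2, 3, 4, 6, 8, 12 h}, or 7 post-dose times with grading at the slit lamp. This assumes that the SAP's time-matched baseline times are also the Day 1 times. The readable pachymetry row of protocol Table 5 includes Day 1, with marks at 1, 2, 4 and 12 h. Subjects also stay overnight; Table 1 footnote d says "They will be admitted to the unit on the morning of Day 1 and discharged from the unit after completing the Day 2 assessments", and Day 2 is itself a slit-lamp visit.

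**7. What cannot be counted.** The slit-lamp row of Table 5 is not in the readable text. A footnote limiting the exam to the morning on named days implies marks at other times, but that is inference and gives no number of exams lost.

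**The case against.** The strongest reply is that this is a visible typographical slip with almost no consequence. The other listed days are all nondosing, the table note says why, and a careful site would see the missing minus sign. Most of what the ungraded exam covers is still viewed after dosing: conjunctiva through redness grading, cornea through haze and staining, anterior chamber through cell and flare. Only lids/lashes/lacrimal, iris and the undilated lens have no graded counterpart. The corneal-haze stopping rule uses a graded scale that footnote c leaves alone. All of this stands and limits the point to minor. It does not make the printed instruction correct.

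A reader might also infer that footnote c conflicts with Section 7.2.2.3. The documents do not support that. The section's visit list is satisfied by a predose exam on Day 1, and its timing is delegated to the tables. Two ordering rules look more promising: "The anterior segment will be examined through the slit lamp before performing IOP measurements, pachymetry, or graded assessments" and "Anterior segment graded assessments should be performed during the slit lamp examination but before IOP measurement". Since those later measurements continue after dosing, one could argue that a structural exam must accompany each round. The argument proves too much. In Cohorts A and B footnote c makes the exam morning-only on Days -2 and -1, yet the SAP has IOP, redness and staining repeated out to 12 h on those days, and pachymetry out to 12 h on Day -1. The same tension would remain in Cohort D after the correction. The rules are better read as fixing the order within a round when the exam is scheduled.

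Nor do the documents support a claim of bias. Active and placebo subjects in Cohort D follow the same table, and no effect on the SAP summaries has been shown.

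**Conclusion.** The text is wrong as written, in a minor way. Footnote c in the two Cohort D tables is inconsistent with its counterparts for Cohorts A to C and with Table 5's own note on nondosing days. Followed literally, it makes one exam type predose only at one of seven dosing-day visits in D2 and D3.

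The 14 subjects (10 active) are planned enrollment, not subjects shown to be affected. The protocol allows cohorts to be dropped, repeated or enlarged, and the documents do not give the status of Cohort D dosing. The conclusion assumes that the printed pages match the readable text and that the Table 5 slit-lamp row carries post-dose marks. If it carries none, the slip has no practical effect on Day 1 and the correction is purely editorial.

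**What to change.** Change Day 1 to Day -1 in footnote c of protocol Table 5 and make the same change in SAP Table 5. Correct the misplaced minus sign in footnote c of protocol Table 4 at the same time, as an editorial matter. If any Cohort D dosing remains, send those sites a short memo stating that the morning-only limit applies to Day -1 and not to Day 1.

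The cost is two footnote corrections, one editorial tidy and, if needed, one memo. No procedure, visit or analysis is added.
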